2.2 Analysis sets

This section defines the populations applicable to this study and their use in the statistical analyses.

Full Analysis Set

The Full Analysis Set (FAS) comprises all patients who received at least one dose of study treatment. The FAS will be the primary population in the assessment of efficacy analysis.

Safety Set

The Safety Set comprises all patients who received at least one dose of study treatment. The Safety Set and FAS are identical in this study. The Safety Set will be the population used in the assessments of safety analysis.

2.2.1 Subgroup of interest

2.2.1.1 Safety

The main analyses on adverse events and abnormal laboratory values will be repeated on the Safety Set in the following subgroups:

- Gender
- Age (< 65 years and ≥ 65 years)

The objective of carrying out these subgroup analyses is to identify safety problems that are limited to a subgroup of patients, or that are more commonly observed in a subgroup of patients.

Summary tables will only be performed on the Safety Set and only if at least 10% of patients are present in each class.

2.2.1.2 Efficacy

For the primary efficacy variable of angiomyolipoma response rate, subgroup analyses will also be performed using the following:

- Gender
- Age (< 65 years and ≥ 65 years)

Efficacy analyses in subgroups are intended to explore the uniformity of any treatment effects found overall. Summary tables will present response rates with the exact 95% confidence interval.

The efficacy analyses in subgroups will be performed on the FAS and only if at least 10% of patients are present in each class (some grouping of classes will be considered for race).

2.3 Patient disposition, demographics and other baseline characteristics

Demographic and other screening data including disease characteristics will be listed and summarized descriptively using the FAS.

Categorical data will be presented as frequencies and percentages. For continuous data, mean, standard deviation, 25th and 75th percentiles, median, minimum, and maximum will be presented.

Basic demographic and background data

All demographic and background data will be listed. The summary table will include age, sex, weight, height, body mass index (BMI), body surface area (BSA), race, ethnicity and WHO performance status.

Qualitative data will be summarized by means of contingency tables, and quantitative data will be summarized by appropriate descriptive statistics (mean, standard deviation, 25th and 75th percentiles, median, minimum, and maximum).

Body surface area in m² will be presented and is calculated using the [\(Dubois and Dubois, 1916\)](#) formula:

$$BSA = (W^{0.425} \times H^{0.725}) \times 0.007184,$$

where W is weight in kilograms and H is height in centimeters.

Diagnosis of TSC disease at Baseline

The diagnosis of TSC-related conditions or symptoms will be documented at the time of screening.

Diagnosis of TSC at baseline will be summarized according to the criteria listed in [Table 2.3-1](#) below.

Table 2.3-1 Diagnostic Criteria for Tuberous Sclerosis Complex (TSC)

Major Features

 1. Hypomelanotic macules (≥ 3, at least 5-mm diameter) 2. Angiofibromas (≥ 3) or fibrous cephalic plaque 3. Ungual fibromas (≥ 2) 4. Shagreen patch 5. Multiple retinal hamartomas 6. Cortical dysplasia 7. Subependymal nodules 8. Subependymal giant cell astrocytoma^a 9. Cardiac rhabdomyoma 10. Lymphangiomyomatosis (LAM)^b 11. Angiomyolipomas (≥ 2)^b
Minor Features

 1. "Confetti" skin lesions 2. Dental enamel pits (>3) 3. Intraoral fibromas (≥ 2) 4. Retinal achromic patch 5. Multiple renal cysts 6. Nonrenal hamartomas

a. Includes tubers and cerebral white matter radial migration lines. b. A combination of the two major clinical features (LAM and angiomyolipoma) without other features does not meet criteria for a definite diagnosis.

Time since initial diagnosis of TSC-related conditions or symptoms will be summarized in years (defined as 365.25 days), and will be measured until the time of baseline (i.e., start date of everolimus).

Medical history

Medical history, including TSC-related conditions and symptoms, will be summarized and listed.

Summaries will be presented by primary system organ class and preferred term. Medical history/current medical conditions are coded using the Medical Dictionary for Regulatory Activities (MedDRA) terminology.

2.3.1 Patient disposition

The FAS will be used for the patient disposition summary tables and listings. Information from the "End of study treatment" will be used to provide a summary showing:

1. Number (%) of patients still on everolimus.
2. Number (%) of patients completed everolimus.
3. Number (%) of patients discontinued everolimus.
4. Primary reason for study treatment discontinuation.
5. Number (%) of patients completed follow-up phase.

6. Primary reason for discontinuation from follow-up phase

2.4 Treatments (study treatment, rescue medication, concomitant therapies, compliance)

2.4.1 Study treatment / compliance

The duration of study treatment (i.e., everolimus) exposure, cumulative dose, dose intensity (DI) and relative dose intensity (RDI) will be summarized. In addition, the duration of exposure to study treatment will be categorized into time intervals, and frequency counts and percentages will be presented for the number of patients in each interval. The number of exposed patients will be summarized by gender and age. The number of patients with dose reductions or interruptions, and the reasons, will also be summarized.

Listings of all doses of the study treatment along with dose change reasons will be produced.

The Safety Set will be used for all summaries and listings of study treatment.

Duration of study treatment exposure

The following algorithm will be used to calculate the duration of study treatment exposure:

$$\text{Duration of exposure (days)} = (\text{date of last administration of study treatment}) - (\text{date of first administration of study treatment}) + 1.$$

The duration includes periods of temporary interruption of study treatment, for any reason. “Date of last administration of study treatment” and “date of first administration of study treatment” were defined in Sections 2.1.1.3 and 2.1.1.2, respectively.

Cumulative dose

Cumulative dose is defined as the total dose given during study treatment exposure, expressed in units of mg. For patients who did not take any study drug, the cumulative dose is by definition equal to zero.

Dose intensity and relative dose intensity

Dose intensity is defined as follows:

$$\text{DI (mg/m}^2\text{/day)} = \text{Cumulative dose (mg/m}^2\text{)} / \text{Duration of exposure (days)}.$$

For patients who did not take any study drug, the DI is by definition equal to zero.

Planned dose intensity (PDI) is the assigned dose by unit of time planned to be given to patients as per protocol in the same dose unit and unit of time as that of the DI. The PDI in this study is 10 mg/day.

Relative dose intensity is defined as follows:

$$\text{RDI} = \text{DI (mg/day)} / \text{PDI (mg/day)}.$$

Cumulative dose, dose intensity and relative dose intensity will be summarized.

Dose reductions and interruptions

The number of patients with dose reductions or interruptions, and the reasons, will be summarized. Dose reductions and interruptions will be determined programmatically using the rules defined below.

Interruption: An interruption is defined as a 0 mg/0 tablets dose given on one or more days.

If the start and end dates of dose interruption are incomplete (partial date), no imputation method will be applied to the date. It will be considered as no dose interruption.

Reduction: A reduction is defined as a decrease in dose to a non-zero dose from the protocol planned dose (10 mg/day), or a decrease from the previous non-zero dose, even if this decrease has been directly preceded by an interruption. For example, in the sequence 10 mg daily – 0 mg – 5 mg daily, the 5 mg daily dose will be counted as a reduction. In the sequence 10 mg daily – 2.5 mg daily – 5 mg daily, two reductions will be counted since the 5 mg daily dose is still lower than the protocol planned dose and is, therefore, counted as a second reduction. A decrease in frequency of administration which results in a lower cumulative dose is also counted as a reduction, e.g., in the sequence 10 mg daily – 5 mg daily – 5 mg every other day, two reductions will be counted.

If a patient moves from a higher than protocol planned dose down to the planned dose then this is not counted as a reduction. However, if they move directly from a higher than planned dose down to a lower than protocol planned dose, or the planned dose on a less frequent regimen, then this is counted as a reduction.

The number of dose reductions and interruptions per patient will be tabulated. The reasons for reductions and interruptions will be summarized, where only reasons that correspond to programmatically determined dose reductions and interruptions will be presented.

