Patients with skin lesions at screening will have digital photos of these lesions taken during screening.

Screening evaluations will also include demography, inclusion/exclusion criteria, relevant medical history/current medical conditions, a physical examination, and vital signs. All

screening evaluations should be completed in the 28 days prior to Treatment Day 1 and after signing the informed consent. A complete list of screening evaluations is provided in the visit evaluation schedule ([Table 7-1](#)). All of the above assessments/procedures must be conducted prior to enrollment.

Open label treatment phase

Patients who meet the study eligibility criteria will start treatment with Afinitor[®]. The treatment duration will be 48 weeks. Patients will have their first daily dose of Afinitor[®] at Day 1 and will continue on treatment until angiomyolipoma progression (as defined in [Section 7.2.1.1](#), an unacceptable toxicity, occurrence of serious protocol deviations, withdrawal of consent or investigator decision to discontinue the patient from study treatment.

Patients with normal liver function will start with a dose of 10 mg/day. Patients with hepatic impairment will start with a dose of 7.5 mg/day (Child-Pugh grade A) or 5 mg/day (Child-Pugh grade B). Dose adjustments (reduction, interruption) will occur based on safety findings. All doses taken by the patient and all dose changes during the study must be recorded on the study treatment CRF.

Safety evaluations are routinely performed at each visit according to the visit schedule ([Table 7-1](#)). Patients must be in a fasting state (at least 12 hours) at the time of blood sampling for all laboratory evaluations including the lipid profile. Hematology, biochemistry and urinalysis evaluations will be performed according to the visit schedule ([Table 7-1](#)). Note that hematology, biochemistry and urinalysis assessments are performed at screening and do not need to be repeated on Day 1 if Day 1 occurs within 14 days of the screening visit. Otherwise, the patient will need to repeat the screening visit blood and urine collections. All blood samples obtained at each visit will be sent to a Central Laboratory for analysis. Urinalysis will be performed locally. If laboratory results are requested on an urgent basis, the attending physician will use the local laboratory results for treatment decisions. Complete details regarding all study required safety assessments are provided in Section 7.

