6.1.1 Dosing regimen

This is a single arm study. All patients except those with impaired liver function will be administered a dose of 10 mg Afinitor[®] orally once daily (Table 6-1) at the same time every day, either consistently with or without food.

Medication labels for study drug will comply with the legal requirements in China and be printed in local language. They will supply no information about the patient. The storage conditions for study drug will be described on the medication label.

Table 6-1 Dose and treatment schedule

Study treatment	Pharmaceutical form and route of administration	Dose	Frequency and/or Regimen
Afinitor [®]	Tablet for oral use	10 mg for patients without hepatic impairment; 7.5 mg for patients with mild hepatic impairment (Child-Pugh grade A) 5 mg for patients with moderate hepatic impairment (Child-Pugh grade B)	Daily

The investigator should promote compliance by instructing the patient to take the study drug exactly as prescribed and by stating that compliance is necessary for the patient's safety and the validity of the study. The patient should be instructed to contact the investigator if he/she is unable for any reason to take the study drug as prescribed.

Tablets

Everolimus will be supplied as 2.5 mg and 5-mg Afinitor[®] tablets. The tablets are packaged in blisters. The tablets should be swallowed whole with a glass of water and should not be chewed or crushed.

For patients with TSC who have SEGA and are unable to swallow tablets whole, the tablet(s) can be dispersed completely in a glass of water (containing approximately 30 mL) by gently stirring until the tablet(s) are fully disintegrated (approximately 7 minutes), immediately prior to drinking. The glass should be rinsed with the same volume of water and the rinse completely swallowed to ensure the entire dose is administered.

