10.3 Treatments (study treatment, concomitant therapies, compliance)

The Safety set will be used for the analyses below. Categorical data will be summarized as frequencies and percentages. For continuous data, mean, standard deviation, median, 25th and 75th percentiles, minimum, and maximum will be presented.

The duration of exposure in weeks to everolimus as well as the dose intensity (computed as the ratio of actual cumulative dose received and actual duration of exposure) and the relative dose intensity (computed as the ratio of dose intensity and planned dose intensity) will be summarized by means of descriptive statistics.

The number of patients with dose adjustments (reduction, interruption, possible dose re-escalation to starting dose, or permanent discontinuation) and the reasons will be summarized for all patients and all dosing data will be listed.

Concomitant medications and significant non-drug therapies prior to and after the start of the study treatment will be listed and summarized according to the Anatomical Therapeutic Chemical (ATC) classification system for all patients.

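### SAP 2.4.1 gives dose intensity in mg/m²/day for a drug dosed in flat mg, in conflict with its own cumulative dose, planned dose intensity and relative dose intensity lines and with protocol 10.3

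*SAP*

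**What the plan says.** SAP 2.4.1 builds the exposure summary in four steps.

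- **Cumulative dose:** "Cumulative dose is defined as the total dose given during study treatment exposure, expressed in units of mg".
- **DI:** the numerator is written "Cumulative dose (mg/m" with a superscript 2, it is divided by the duration of exposure in days, and the result is labelled mg/m²/day.
- **PDI:** the planned dose per unit of time, "in the same dose unit and unit of time as that of the DI. The PDI in this study is 10 mg/day".
- **RDI:** DI divided by PDI, with both labelled mg/day.

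The section closes by saying that cumulative dose, DI and RDI will each be summarized, so DI is a reported result in its own right.

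Protocol 10.3 describes DI as "computed as the ratio of actual cumulative dose received and actual duration of exposure" and makes no mention of body size. Dosing is in flat mg. Protocol 6.1.1 states: "All patients except those with impaired liver function will be administered a dose of 10 mg Afinitor". Protocol 4.1 gives the remaining starting doses, also in flat mg: "Patients with hepatic impairment will start with a dose of 7.5 mg/day (Child-Pugh grade A) or 5 mg/day (Child-Pugh grade B". SAP section 4 declares no change from the protocol's analyses.

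**The concern.** The DI line disagrees with the lines on either side of it. Its numerator is not the quantity defined just above it, its unit is not the one the PDI is said to share, and it is not the unit the RDI line expects. No dose in this trial is scaled to body size, so mg/m² has no natural meaning here. A per-m² DI would also be an undeclared departure from protocol 10.3.

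The formula could still be programmed. SAP 2.3 derives BSA by the DuBois formula for the demographic table, so the variable will exist. SAP 2.4.1 does not say whether baseline or later weight would apply, although the protocol's visit schedule collects weight at every treatment visit. Two programmers could therefore produce different DI tables.

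Safety is the primary objective, and DI and RDI describe the exposure behind the adverse event incidence. A DI table that mixes dose taken with body size describes that exposure poorly.

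**Working it through.** **Inputs from the documents.** Daily dose 10 mg (protocol 6.1.1). Planned duration 48 weeks = 336 days (protocol 6.1.2). PDI 10 mg/day (SAP 2.4.1). BSA = W^0.425 × H^0.725 × 0.007184, with W in kg and H in cm (SAP 2.3).

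**Assumed inputs.** The documents give no weights or heights, so body sizes are assumed and shown as a range.

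**1. The plan's own figure, in mg.** Cumulative dose = 10 × 336 = 3360 mg. DI = 3360 / 336 = 10 mg/day, equal to the stated PDI. RDI = 10 / 10 = 1.00. This is the result when the SAP's mg cumulative dose and its mg/day RDI line are followed.

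**2. DI by its own formula.** For the same fully dosed patient, DI = 3360 / (BSA × 336) = 10 / BSA. The last column shows RDI only for the case where this DI is then divided by 10.

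| Assumed size | BSA (m²) | DI (mg/m²/day) | RDI if this DI is reused |
|---|---|---|---|
| 40 kg, 150 cm | 1.30 | 7.7 | 0.77 |
| 50 kg, 155 cm | 1.47 | 6.8 | 0.68 |
| 60 kg, 165 cm | 1.66 | 6.0 | 0.60 |
| 80 kg, 175 cm | 1.96 | 5.1 | 0.51 |
| 90 kg, 180 cm | 2.10 | 4.8 | 0.48 |

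Duration cancels, so these figures do not depend on the 336 days.

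**3. What the per-m² DI responds to.** It is cumulative dose / (BSA × days), so it still falls when doses are missed or reduced. At 60 kg and 165 cm, 5 mg daily throughout gives 5 / 1.66 = 3.0, half of the 6.0 for full dosing. Body size is added to the variation and does not replace dosing. The two are then hard to separate: a fully dosed patient of 80 kg (5.1) matches a 40 kg patient averaging 5.1 × 1.30 = 6.6 mg/day.

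**4. Which line is out of step.** The cumulative dose definition, the PDI, the RDI line, the dose-reduction rules in SAP 2.4.1 (which use a planned 10 mg/day), the flat dosing and protocol 10.3 all work without body size. Only the DI formula uses mg/m².

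**The case against.** The strongest reply is that one formula carries stray unit labels and the rest of the section shows what is meant. SAP 2.4.1 nowhere instructs anyone to divide by BSA and names no BSA to use. To obtain mg/m², a programmer would have to override the stated definition of cumulative dose. DI and RDI enter no endpoint calculation. The SAP also reports cumulative dose in mg, lists all doses with reasons for change, and tabulates reductions and interruptions.

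Most of this stands, and it rules out three stronger readings that a reader might infer.

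- **That the SAP would give a fully dosed patient an RDI of about 0.5 to 0.7.** The RDI line calls for DI in mg/day, and programmed from that line the RDI is 1.00. The lower values need the per-m² DI to be reused, contrary to that line.
- **That the DI table would reflect body size instead of adherence.** Step 3 of the working shows that it would still respond to missed and reduced doses.
- **That the safety profile would be read as arising at half to two-thirds of the planned dose.** This needs a miscomputed RDI that nobody notices beside the mg cumulative dose and the dose-reduction tables, where it would look plainly wrong.

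The reply does not remove the fault in DI itself. The mg/m² unit appears on both sides of the only DI formula in the SAP, and DI is summarized separately from RDI. The intended unit can be inferred, but the text as written specifies another one.

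**Conclusion.** The point holds as a unit inconsistency in SAP 2.4.1. The contradiction can be read directly from the text and rests on no assumption. Its numerical size does rest on one: the DI range of about 5 to 7 mg/m²/day for full 10 mg dosing, or 4.8 to 7.7 over the wider set, depends on assumed body sizes. The RDI error is conditional on the per-m² DI being carried forward, and its size depends on the same assumed body sizes.

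The consequence is confined to the descriptive exposure tables. Adverse event and laboratory incidences, the angiomyolipoma response rate and its confidence interval do not use DI or RDI. This is a minor specification error that should be corrected because the correction is cheap and the tables give context to the primary safety results.

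**What to change.** In SAP 2.4.1, replace the DI formula with: DI (mg/day) = cumulative dose (mg) / duration of exposure (days). Remove mg/m² and keep DI, PDI and RDI in mg/day throughout. This agrees with protocol 10.3 and makes the section's four definitions consistent.

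Check that the exposure program takes cumulative dose in mg and uses no BSA. SAP 2.7.1 already refers to what was observed at database lock, so any DI and RDI tables already produced should be checked as well. A quick test is that a patient with 10 mg recorded on every day shows DI 10 mg/day and RDI 1.00.

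The cost is one line of SAP text and a short program check. No new data are needed.

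### SAP 2.4.1 dose-change rules can misstate the descriptive exposure tables: some upward steps count as reductions, undated interruptions are dropped, planned dose is fixed at 10 mg/day, and re-escalation is left out

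*SAP*

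**What the plan says.** **Reductions.** SAP 2.4.1 states "A reduction is defined as a decrease in dose to a non-zero dose from the protocol planned dose (10 mg/day", with a fall from the previous non-zero dose as a second way to qualify. It then gives an example: "In the sequence 10 mg daily – 2.5 mg daily – 5 mg daily, two reductions will be counted". The reason offered is that 5 mg is still under the planned dose. Two further clauses follow: "A decrease in frequency of administration which results in a lower cumulative dose is also counted as a reduction", and "If a patient moves from a higher than protocol planned dose down to the planned dose then this is not counted as a reduction".

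**Interruptions.** An interruption is a 0 mg dose on one or more days. However, "If the start and end dates of dose interruption are incomplete (partial date), no imputation method will be applied to the date". The next sentence reads: "It will be considered as no dose interruption".

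**Reasons.** These are summarised, "where only reasons that correspond to programmatically determined dose reductions and interruptions will be presented". Separately, "Listings of all doses of the study treatment along with dose change reasons will be produced".

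**Dose intensity.** The same section defines planned dose intensity (PDI) as the dose assigned under the protocol, then sets it at 10 mg/day. Relative dose intensity (RDI) is dose intensity (DI) divided by PDI. Protocol 6.4.2 has the investigator assign 10, 7.5 or 5 mg once daily by hepatic function.

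**Re-escalation.** Protocol 10.3 plans a summary of patients with dose adjustments and lists return to the starting dose as a category distinct from reduction. SAP 2.4.1 has no such summary, and SAP section 4 declares no change to the protocol.

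**The concern.** The primary objective is safety, and the exposure tables show how well patients stayed on drug while the safety data accrued. Four features of the rules can put wrong entries in them.

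- A step up that stays below 10 mg/day is counted as a further reduction, and the reason for raising the dose can be tabulated as a reason for lowering it.
- Missing dates make the length of an interruption uncertain, not its occurrence, yet the rule removes the event and its reason. SAP 2.8.1 also tabulates adverse events requiring dose adjustment or interruption, for which Protocol 8.1.1 records the action taken with each event. One patient could therefore appear as interrupted there and as uninterrupted in the exposure table.
- A single planned dose of 10 mg/day conflicts with the SAP's own definition of PDI and with the protocol's three assigned doses.
- A planned summary is dropped without being declared.

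**Working it through.** **Inputs.** The reduction, interruption, PDI and RDI rules are from SAP 2.4.1; assigned doses from Protocol 6.4.2; 48 weeks (336 days) from Protocol 6.1.2; 40 treated patients from the Amendment 2 rationale. The study is descriptive, so no test or power formula applies.

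**Reduction counts.** Each regimen is expressed as average daily dose, so 5 mg every other day is 2.5 mg/day. SAP rule: a change to a non-zero dose counts if the new dose is below 10 mg/day or below the previous one, except a move from above plan to plan. Falls-only rule: count only if the average daily dose is below that of the previous non-zero regimen, with the same exception. The first three rows are the SAP's own examples, which the coded rule reproduces.

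| Sequence (mg) | SAP rule | Falls only |
|---|---|---|
| 10, 0, 5 | 1 | 1 |
| 10, 2.5, 5 | 2 | 1 |
| 10, 5, 5 every other day | 2 | 2 |
| 10, 5, 2.5, 5 | 3 | 2 |
| 10, 5, 5 every other day, 5 | 3 | 2 |
| 10, 5, 10 | 1 | 1 |
| 10, 20, 10 | 0 | 0 |
| 10, 20, 5 | 1 | 1 |

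The two rules part only when the dose rises and stays below 10 mg/day. A 10 mg starter who reaches that point has already had a true reduction, so the number of such patients with any reduction does not change.

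The 10, 5, 2.5, 5 sequence is possible under Protocol 6.3: a patient already at 5 mg daily has the dose halved for a moderate CYP3A4/PgP inhibitor and later returned to the prior dose.

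For lower assigned doses the fixed 10 mg reference adds counts: 7.5, 5, 7.5 gives 2 against 1, and 5, 5 every other day, 5 gives 2 against 1. In both, return to the assigned starting dose is counted as a reduction.

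**Interruptions.** One recorded event becomes 0. A patient with no other datable interruption moves the proportion interrupted by 1/40 = 2.5 percentage points, always downward.

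The SAP does not say whether such days contribute 0 mg or the last dose. As an illustration, assume 28 undated days off treated as dosed at 10 mg: DI = 3360/336 = 10.0 mg/day. With those days at zero, DI = 10 × (336 − 28)/336 = 9.17 mg/day.

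**RDI at full compliance, PDI fixed at 10 mg/day.**

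- Assigned 7.5 mg: 7.5 × 336 = 2520 mg; 2520/336/10 = 0.75.
- Assigned 5 mg: 5 × 336 = 1680 mg; 1680/336/10 = 0.50.
- With PDI equal to the assigned dose, both are 1.00.
- Fall in mean RDI per such patient: 0.25/40 = 0.00625, or 0.50/40 = 0.0125.
- Assumed range, everyone fully compliant: one such patient gives mean RDI 0.994 (7.5 mg) or 0.988 (5 mg); four give 0.975 or 0.950.

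**The case against.** **The reduction rule is a disclosed convention.** It is predefined, explained by example and reproducible. The number of patients with any reduction, which both SAP 2.4.1 and Protocol 10.3 name, is unchanged for 10 mg starters. The step from 10 to 2.5 mg is not in Protocol Table 6-2, the inhibitor route is uncommon, and the ordinary 10, 5, 10 course is counted correctly. All this stands and limits the weight. It does not rescue the rule: the SAP also tabulates reductions per patient and their reasons, and it scores partial recovery to 5 mg daily (3) above remaining at 5 mg every other day (2).

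**The date rule is narrow and has safeguards.** It speaks of start and end dates together; whether one incomplete date is enough is unclear. Data queries (Protocol 9.4) should make such records rare, and the dose listing keeps them. An undated 0 mg record may also be 0 mg entered after permanent discontinuation, so counting every such record could overcount. That is a fair limit on the remedy. Neither safeguard corrects the summary table.

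**The fixed 10 mg may affect nobody.** Exclusion criteria 5 and 16c in Protocol 5.3 may leave few or no patients with hepatic impairment. Child-Pugh grade is in neither the visit schedule (Table 7-1) nor the laboratory plan (Table 7-5), so the assigned dose needs another source. Both points stand; the internal contradiction remains.

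**Stronger inferences.** A reader might infer that a patient who stays on an assigned 7.5 or 5 mg is counted as reduced. That requires comparing the first dose with 10 mg, and no SAP example does so; every example starts at 10 mg. A reader might also infer that the tables are in fact wrong. The documents give no counts of affected patients.

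**Conclusion.** The concern holds as a defect in stated rules whose realised effect is unknown. The first rule can only overstate reductions per patient, by one for each upward step that stays below 10 mg/day. The second can only understate interruptions, by 2.5 points per affected patient with no other datable interruption. Fixing PDI at 10 mg/day turns full compliance at 7.5 or 5 mg into an RDI of 0.75 or 0.50. The re-escalation summary is a small undeclared omission.

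The number of affected patients is not given and may be zero for the date rule and the PDI rule; no frequency is available for the upward-step rule.

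The documents do not support extending this to the main results. The adverse event, laboratory and response endpoints do not use these rules, and every dose and change reason is still listed. Nor can cumulative dose, DI and RDI be called safe from the date rule: they may be affected, since the dosing of undated days is unspecified. The point merits correction because the rules are explicit and cheap to change, not because a material effect has been shown.

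**What to change.** 1. Count a reduction only when the average daily dose (dose times frequency) falls below that of the previous non-zero regimen. Keep the exception for a move from above plan to plan. Tabulate upward steps separately, including the return to starting dose planned in Protocol 10.3.
2. Count a recorded 0 mg interruption, with its reason, even when its dates are partial, provided it is recorded as temporary and not as 0 mg after permanent discontinuation. Leave its duration missing and state how its days enter cumulative dose, DI and RDI.
3. Reconcile PDI and the reduction reference with the protocol's assigned starting doses, and name the field that supplies the assigned dose, for example the starting dose prescribed on the Study Treatment CRF. Counting a first dose below the assigned start as a reduction works only if that field is independent of the first dose; if the assigned dose is inferred from the first dose, omit that condition.
4. Editorial: label DI in mg/day. It is now written in mg/m²/day, while cumulative dose is in mg and the RDI formula uses mg/day.

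The cost is SAP wording and derivation code, with no new data collection provided the assigned dose can be taken from a field already recorded. Because SAP 2.7.1 already describes results seen at database lock, record the change as a dated post-lock correction and show both counts where they differ.
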